2.3 Study Design

We will conduct a two-arm randomized, wait-list control study. We will recruit 610 participants total: 600 patient participants and 10 staff participants. We will recruit 600 smokers to complete a 9-week intervention that integrates financial management and smoking cessation counseling. Participants will be randomized (300 per arm, stratified by site) to receive the intervention immediately after enrolling (Intervention Arm) or 6 months later (Waitlist Control Arm). Both arms will receive nicotine replacement therapy (NRT) for four weeks as part of their time in integrative counseling. We will survey participants at baseline, 6 months and 12 months to assess outcomes and their satisfaction with treatment. The first 150 enrollees will complete an additional 2 month follow up survey. Additionally, we will recruit and interview hospital staff (N=5 per site, 10 total) to assess their perceptions regarding barriers and facilitators toward downstream implementation of the intervention.

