4.6.2 Control Arm: Waitlisted Integrated Smoking Cessation and Financial Counseling

Six months after enrolling, participants randomized to the Control Group will receive all of the services described in the Intervention Group section above. Starting 3 weeks before their 6-month time point, study staff will call patients to schedule a counseling appointment (Appendix I). Patients in the control arm will not receive any procedures or counseling in the first six months.

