4.6.4 Both Arms: Patient Participant Follow-up Surveys

We will conduct a telephone follow-up survey 6 months (Appendix F) and 12 months (Appendix G) after enrollment with all participants. A study team member will make 10 attempts over 4 weeks to complete the survey (Appendix J). We will mail a hard copy or email the survey if participants do not want to complete the survey over the phone. The surveys will re-assess participant behavior and characteristic assessed at baseline, and a short series of close-ended and open-ended questions about satisfaction with the interventions. The first 150 participants will complete an additional 2 month follow up survey (Appendix E) in order to obtain preliminary data. After the first 150 enrollments, the 2 month survey will be retired and the remainder of the 450 enrollments will only complete surveys at baseline, 6 months and 12 months. All enrollees that signed a consent form indicating the additional 2 month survey will be eligible to participate in that survey and will be compensated accordingly. Participants will be paid \$15 as reimbursement for their time completing the surveys. The additional follow-up survey (Appendix S) to gain feedback from participants who are NYCHA-residents on their smoking cessation needs will be conducted via phone. Patients being contacted are already enrolled in the study.

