5.1 Data Analysis

To evaluate the acceptability and feasibility of the integrated intervention, we will calculate the number of counseling sessions completed and satisfaction with treatment, which we will summarize descriptively using count and frequency statistics. We will calculate additional measures of study feasibility and acceptability, including the eligibility rate among people screened, enrollment rate among those eligible, reasons for ineligibility or refusal, and the proportion of participants who would recommend the intervention to other smokers. To estimate the effect of the integrated intervention on outcomes we will use generalized estimating equations (GEE) to model the main effects of time (baseline to 6 and 12 months)

and treatment group, and the interaction of time and treatment, on each outcome. GEE will allow us to determine whether intervention effects are present and whether they change over time.

We will also calculate and sum all time and costs of administering the interventions. Each intervention staff member will record their activity in a web-based intervention tracking system (using REDCap). Staff prospectively input detailed information for a 1-week sample of their activities and associated time required on a monthly basis. Those recording their time and activities have flexibility to add or tailor their entry form to match their exact activities. We will assign a dollar value for each unit of staff time based on the wage and fringe rate of those who perform the activity using regional labor rates from the US Bureau of Labor Statistics. We will also keep track of medications ordered and used by participants, which we will assign a dollar value to using Red Book, a wholesale pharmaceutical pricing index. Once all costs are compiled and summed, they will be adjusted to constant dollars using the medical care component of the Consumer Price Index.

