5.2 Data Monitoring Plan

This study will not have an external data monitoring board. The PI will monitor treatment fidelity on a weekly basis by holding meetings with the study counselors to review active patients. Counselors will also keep standardized, electronic documentation of every counseling session in a REDCap database created for the study, which will be reviewed weekly with the PI. To ensure accuracy of survey data, all paper surveys will be entered twice into study databases, and the two entries will be compared for consistency. Inconsistencies in data entry will be resolved by a third review of the paper survey records. The study team (PI, Co-Is, Research Coordinator) will monitor the quality of patient survey data on a quarterly basis by running data reports showing survey responses rates, as well as missing or invalid values. In addition, to allow for monitoring of adherence to survey procedures, the RAs will use a REDCap database created for the study to document all patient contacts and procedures completed with a patient. The PI and Research Coordinator will monitor adherence to data collection procedures by reviewing monthly REDCap procedure reports. Protocol deviations (either counseling or survey data collection deviations) will be reported to the NYU IRB as per the reporting requirements.

Study staff will document adverse events in a REDCap database created for the study. Adverse events will be monitored daily by the PI. Any adverse event (AE) identified by a study team member (e.g., counselor, RA,) will be reported to the PI within 24 hours. The PI will determine whether the event is a) serious or non-serious; b) anticipated or unanticipated, and c) related to the study or unrelated to the study. The PI will ensure that any necessary actions are taken immediately to address the current patient situation, and then will decide if the team needs to make any changes in the protocol and/or consent forms to prevent future occurrences or better inform future participants. We will report the event to the NYU IRB as per the reporting requirements. Violations of patient privacy/confidentiality will be treated as an AE related to the study and will be addressed immediately as appropriate.

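### The 6-to-12-month change in the arm difference cannot show whether the effect changes over time, because controls receive the programme from month 6 and Section 5.1 states no assumption that separates the two

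*Combined protocol and SAP*

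**What the plan says.** Section 2.3 sets the design: "We will conduct a two-arm randomized, wait-list control study", with 300 participants per arm, stratified by site. Section 4.6.2 describes the control arm in two statements that matter here. Before month 6: "Patients in the control arm will not receive any procedures or counseling in the first six months". From month 6: "Six months after enrolling, participants randomized to the Control Group will receive all of the services described in the Intervention Group section above". Section 4.6.4 surveys everyone at 6 and 12 months after enrolment, whichever arm they are in.

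Section 5.1 is the only analysis text. For each outcome it fits a GEE with main effects of time (baseline, 6 and 12 months) and group, and their interaction. It then states the inference: "GEE will allow us to determine whether intervention effects are present and whether they change over time".

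Section 5.1 does not mention that controls start the programme between the two follow-up surveys. It does not restrict the effect estimate to month 6, describe the 12-month contrast as early against late start, recode exposure for controls after month 6, or state how the delayed programme is assumed to work.

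**The concern.** The sentence in Section 5.1 makes two claims. The first, that the model can show whether an effect is present, is supported by the 6-month comparison, where one arm has been offered the programme and the other has not. The second, that it can show whether the effect changes over time, needs a comparison at month 12 with people who have not had the programme. By then no such arm exists. The programme lasts 9 weeks (Section 2.3). A control who starts on time at month 6 therefore has about 26 − 9 = 17 weeks between the end of the programme and the 12-month survey.

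Aim 1 (Section 2.2) is to estimate the programme's effect on income, savings, financial stress, mental wellness and abstinence. If the arm difference narrows from month 6 to month 12, a reader following Section 5.1 would take it as a change in effect. The same narrowing would appear if the effect lasted and the programme also worked in controls.

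**Working it through.** The plan gives no power, error rate, effect size or expected rate, so there is no figure of its own to reproduce. The check is one of identification, followed by an illustration.

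**Unknowns.** Baseline mean b, common to both arms by randomisation; background change s6 and s12 at months 6 and 12; effect in immediate starters e6 and e12; benefit c that controls have gained by month 12.

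| | Baseline | Month 6 | Month 12 |
|---|---|---|---|
| Intervention | b | b + s6 + e6 | b + s12 + e12 |
| Control | b | b + s6 | b + s12 + c |

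**Contrasts.**
- Month 6: D6 = e6.
- Month 12: D12 = e12 − c.
- Change: D12 − D6 = (e12 − e6) − c.

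The change in the arm difference misses the change in effect by exactly c. The two agree only if controls gain nothing.

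**Separate arm means do not settle it.** The two baseline cells share one expected value, so there are five distinct means for six unknowns (rank 5 of 6). D6, D12 and D12 − D6 are estimable; e12 and e12 − e6 are not. Example with assumed abstinence percentages:
- A: b = 0, s6 = s12 = 8, e6 = e12 = 7, c = 7. Intervention 0, 15, 15; control 0, 8, 15. True change in effect: 0.
- B: b = 0, s6 = 8, s12 = 15, e6 = 7, e12 = 0, c = 0. Intervention 0, 15, 15; control 0, 8, 15. True change in effect: −7.

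Both give D12 − D6 = 0 − 7 = −7. More participants would not separate them.

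**Assumptions that would identify the change.**
- No background change after month 6 (s12 = s6): e12 − e6 is the within-arm change in the intervention arm, an uncontrolled quantity.
- Delayed starters respond as immediate starters did (c = e6): D12 = e12 − e6, so the answer is the 12-month arm difference itself, while D12 − D6 = e12 − 2·e6.

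Section 5.1 states neither, and the two point to different contrasts.

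**Illustration (all inputs assumed except 300 per arm).** Unit SD, equal correlation ρ between visits, constant effect 0.30 SD, two-sided 5% test, no loss to follow-up. SE of D12 − D6 = √[(2/n) × 2(1 − ρ)]. With n = 300 and ρ = 0.5, SE = √(2/300) = 0.0816.
- Full catch-up (c = 0.30): D12 − D6 = −0.30, 95% CI −0.46 to −0.14; 0.30/0.0816 = 3.67; rejection Φ(3.67 − 1.96) = 96%.
- Half catch-up (c = 0.15): −0.15, 95% CI −0.31 to 0.01; 0.15/0.0816 = 1.84; rejection Φ(1.84 − 1.96) = 45%.
- No catch-up: 5%.

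| Rejection, true change 0 | Full catch-up | Half catch-up |
|---|---|---|
| n = 300, ρ = 0.3 | 87% | 34% |
| n = 300, ρ = 0.5 | 96% | 45% |
| n = 300, ρ = 0.7 | >99% | 66% |
| n = 210 (70% followed), ρ = 0.5 | 87% | 34% |

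A binary version (assumed 8% untreated abstinence at both visits, 300 per arm, ρ from 0.3 to 0.7) gives, for a constant 8-point effect, 67% to 95% with full control gain and 24% to 47% with half. For a constant 5-point effect with full gain it gives 36% to 68%.

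**The case against.** The best defence is that the fault lies in the wording more than the model. Section 5.1 does not say that the 6-to-12-month change will be the test. A time-by-group model with these visits yields both the 6- and 12-month contrasts. Section 4.6.2 gives controls the same services, so assuming that they respond like immediate starters is natural, and the 12-month contrast would then be the change in effect. This stands, and it makes the correction cheap. It does not rescue the sentence, because the assumption is unstated and the contrast that follows from it is not the interaction change a reader would look at.

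A second defence is that example B needs untreated abstinence to rise by just enough to offset the lost effect. That is fair: B shows non-identification, not a likely course. If background were flat, fading would show as a fall in the intervention arm and catch-up as a rise in controls.

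A third is that this is a pilot whose aim is to estimate effects, and its main randomised estimate survives. That limits the severity.

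A reader might infer more than the documents support:
- *That the 12-month comparison is invalid.* It is a sound randomised comparison of immediate with six-month-delayed delivery; only its label is at issue.
- *That the 6-month effect is contaminated.* Controls are to receive nothing before month 6. Survey attempts may run over 4 weeks (Section 4.6.4), and no available text places the survey before a control's first session. However, the scheduling and contact procedures are in Appendices I and J, which are not available here. This is a query, not a finding.
- *That the trial will falsely report fading 96% of the time.* Every input to that figure except the arm size is assumed.

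**Conclusion.** The second half of the Section 5.1 claim does not hold as written and should be corrected. With controls treated from month 6, the 6-to-12-month change in the arm difference equals the change in effect minus the control benefit. Without a further assumption, fading cannot be separated from control catch-up. That conclusion and the size of the bias (exactly c) rest only on the design, not on assumed rates. The rejection rates are illustrative.

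The 6-month arm contrast remains the estimate of the programme's effect against no programme, provided that controls are surveyed before their first session.

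**What to change.** Amend Section 5.1 as follows.

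1. Name the 6-month arm contrast as the estimate of the intervention effect, adjusted for baseline where the baseline value varies. For abstinence, use the plain month-6 contrast. Section 3.5.1 requires smoking in the past 30 days, so baseline abstinence may be zero in both arms; a group-by-time term on a logit scale is then not estimable. The plan gives neither the link nor the abstinence definition, so this point is conditional.
2. Report the 12-month arm contrast as immediate versus six-month-delayed delivery, not as persistence or change of effect.
3. Describe the 6-to-12-month course in the intervention arm as uncontrolled and descriptive. If a change in effect is still to be estimated, state the identifying assumption and the contrast that goes with it.

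As a secondary query, count the controls whose 6-month survey came after their first session. Section 5.2 (Data Monitoring Plan) already provides the records: "Counselors will also keep standardized, electronic documentation of every counseling session in a REDCap database created for the study", and research assistants log participant contacts in REDCap as well.

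The cost is a few sentences and one tabulation, with no extra participants, visits or data items. The downside is that the 12-month comparison loses a claim that the design does not support without an added assumption.

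### The only effect analysis is a GEE with no method for survey non-response; at month 6 it is exposed to bias if who responds differs by arm, and baseline data already collected could address part of this

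*Combined protocol and SAP*

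**What the plan says.** Section 5.1 gives one inferential method: "To estimate the effect of the integrated intervention on outcomes we will use generalized estimating equations (GEE) to model the main effects of time". The model's other terms are arm and the arm-by-time product, and the same model is applied to every outcome over the three surveys. The section then claims that "GEE will allow us to determine whether intervention effects are present and whether they change over time". Weights, covariates, working correlation, analysis set, treatment of non-responders and sensitivity analyses are not mentioned. The Data Monitoring Plan (5.2) refers to missing values only as something the team will look at in quarterly data-quality reports.

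Outcomes are collected by survey (4.6.4): "We will conduct a telephone follow-up survey 6 months (Appendix F) and 12 months (Appendix G) after enrollment with all participants". Effort is the same in both arms: "A study team member will make 10 attempts over 4 weeks to complete the survey", with mail or email for those who decline the telephone.

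Other contact near month 6 is not the same. For controls only, 4.6.2 says: "Starting 3 weeks before their 6-month time point, study staff will call patients to schedule a counseling appointment". Controls have had no procedures before then, and their counseling and NRT are still ahead. Intervention participants begin their nine-week program on enrollment (4.6.1) and have no comparable call described around month 6.

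**The concern.** If nothing more is specified, a GEE is fitted to the responses that were obtained. Its terms are arm, time and their product, so it makes no use of baseline characteristics that may predict who answers.

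Controls near month 6 have a reason to stay in touch, whatever their smoking status. Intervention participants would normally have finished months earlier, and whether they answer could depend more on readiness, mood, financial stress or whether they quit. If so, responders would be a differently selected group in each arm.

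Month 6 matters most because it is the last survey before controls are treated, and the only such survey taken by all participants. Selection there passes directly into the between-arm comparison of abstinence and the financial outcomes, which Aim 1 (2.2) sets out to estimate.

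**Working it through.** The plan states no power, alpha, event rate or expected response, so it has no figure to reproduce. From the documents: 300 per arm (2.3), surveys at 6 and 12 months (4.6.4), and the model terms (5.1). Every rate below is an assumption. True abstinence is 10% in both arms unless stated, and tests are two-sided at 5%.

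**1. Response depends on arm only** (70% intervention, 80% control). Responders are a random subset of each arm, so the expected rates stay at 10.0% vs 10.0%. Bias is 0 and the simulated type I error is 5.0%. For a continuous outcome, the month-6 GEE interaction was 0.001 SD (truth 0, simulation error 0.004).

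**2. Response depends on a baseline factor, in the intervention arm only.** Suppose half the participants have the factor. Intervention response is 80% with it and 60% without; control response is 78% throughout. Abstinence is 15% with the factor and 5% without, averaging 10%.

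- Intervention responders: (0.5×0.80×0.15 + 0.5×0.60×0.05) / (0.5×0.80 + 0.5×0.60) = 0.075 / 0.70 = 10.7%.
- Control responders: 10.0%. Bias = +0.7 points.
- Weighting each responder by 1/response probability: 0.5×0.15 + 0.5×0.05 = 10.0%. Bias = 0.
- Range: abstinence of 12%/8% gives 0.072/0.70 = 10.3% (+0.3); 18%/2% gives 0.078/0.70 = 11.1% (+1.1).

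The working correlation does not rescue abstinence. Everyone must have smoked in the past 30 days (3.5.1), so baseline abstinence carries little or no information. A simulation with these inputs (15%/5%), baseline abstinence set to zero and an identity-link GEE (six runs of 20,000) gave month-6 interactions of +1.0 points (independence), +0.9 (exchangeable) and +0.2 (weighted). Simulation error was about 0.14 points. Compared with the weighted fit on the same data, the unweighted fits are about 0.7 and 0.6 points too high.

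For a continuous outcome the choice can matter. With intervention-arm response depending on the observed baseline outcome, and no true effect, the interaction was -0.079 SD (independence), -0.003 (exchangeable) and -0.001 (weighted). The plan does not say which structure it would use.

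**3. Response depends on the outcome.** The responder rate is p·rq / (p·rq + (1-p)·rs), where p is true abstinence and rq, rs are the response probabilities of abstainers and smokers.

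| Intervention rq/rs | Control rq/rs | Responder rates | Bias | Type I error |
|---|---|---|---|---|
| 80%/70% | 80%/70% | 11.3% vs 11.3% | 0 | 5.0% |
| 80%/70% | 80%/80% | 0.080/0.710 = 11.3% vs 10.0% | +1.3 points | 7.4% |
| 85%/65% | 80%/80% | 0.085/0.670 = 12.7% vs 10.0% | +2.7 points | 14.0% |

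In the last pattern, a true 17% vs 10% would appear as 0.1445/0.6840 = 21.1% vs 10.0%: 11.1 points instead of 7.0.

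**4. Counting non-responders as smokers is not a neutral repair.** With 70% vs 80% response by arm and a true 17% vs 10%, it gives 0.17×0.70 - 0.10×0.80 = 0.119 - 0.080 = 3.9 points instead of 7.0.

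**The case against.** The strongest reply is that this is non-specification and not a wrong method. Section 5.1 nowhere says that the GEE is unweighted or restricted to responders. That is correct: both are the default reading of a silent plan. But nothing elsewhere brings predictors of response into the analysis, so run as written it is an available-case analysis.

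A reader might infer that the GEE is valid only if response is completely at random. That is too strict: step 1 shows no bias when response depends on arm alone. For the same reason a reader should not infer that unequal contact is itself a bias. It matters only if it changes which participants answer, differently by arm, and the documents contain no evidence that it does. Survey attempts, fallback modes and the $15 payment are the same in both arms, and staff also check medical records for updated contact details (4.6.5).

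It would also be wrong to call month 6 the only follow-up with untreated controls. The first 150 enrollees have a 2-month survey (2.3, 4.6.4).

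Finally, the type I errors in step 3 might be read as an argument for imputation. They are not. Response there depends on the outcome itself, which imputation or weighting from baseline data would not in general remove. Only step 2 supports the change of primary method; step 3 supports the sensitivity analyses. The step 2 bias is also modest: 0.7 points against a standard error of √(0.1×0.9/210 + 0.1×0.9/234) = 2.9 points, using 70% and 78% of 300.

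**Conclusion.** The point holds in this form. The planned GEE is unbiased when response depends only on arm and time, and generally biased when response depends, differently by arm, on baseline factors outside the model or on the outcome. The second situation is plausible at month 6 because of the arm-specific circumstances there, but the documents do not show that it will occur. Its size cannot be determined without response rates. Under the assumed patterns the bias in abstinence is about 1 to 3 points: +0.7 (range +0.3 to +1.1) when response depends on a baseline factor, and +1.3 to +2.7 when it depends on the outcome. Pilot status does not remove the concern, since Aim 1 is to estimate these effects in 600 randomized participants. Choosing a method after seeing response by arm would leave room for selective analysis.

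**What to change.** In Section 5.1:

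- Make the primary analysis multiple imputation carried out separately by arm, followed by the planned GEE. The imputation model should use the baseline survey variables in 4.4 (tobacco use, readiness to quit, income, financial stress, mood), site, and outcomes from the other visits. Inverse-probability-weighted GEE with the same information is an acceptable alternative; name one in advance.
- State the missing-data assumption and the working correlation.
- Report survey response by arm at each time point.
- For abstinence, add two sensitivity analyses to cover response that depends on the outcome itself: missing counted as smoking, and a delta-adjusted tipping-point analysis. Missing counted as smoking should not be primary, for the reason in step 4.

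The cost is wording and a modest amount of analysis, with no new data. The small downside is that results then depend on an imputation or weighting model, which should be written down before response by arm is examined.

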2.2 Aims

1. Estimate the acceptability of the integrated program and its effect on participants' disposable income, savings, financial stress, mental wellness, and abstinence from cigarettes.
2. Estimate the per-patient cost of the integrated program.
3. Identify barriers and facilitators toward wide-scale implementation of the program model.

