3.1 Number of Subjects

We will recruit 610 participants total. 600 recruited participants will be smokers enrolled from any of our recruitment methods outlined in "Patient Participant Recruitment" below. Half of the enrolled participants (300 smokers) will receive the intervention immediately after consent, and the other 300 will receive the intervention after 6 months. Additionally, we will recruit 10 staff participants: 5 staff from Bellevue Hospital and 5 staff from NYU Lutheran.

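### Does Aim 2's per-patient cost need a stated denominator and a stated rule for scaling up the monthly one-week time samples?

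*Combined protocol and SAP*

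**What the plan says.** Section 2.2 Aims sets the target of Aim 2: "Estimate the per-patient cost of the integrated program". The only costing method is in section 5.1 Data Analysis, which opens with "We will also calculate and sum all time and costs of administering the interventions". Staff time comes from a tracking system: "Staff prospectively input detailed information for a 1-week sample of their activities and associated time required on a monthly basis". Time is priced at regional wage and fringe rates, medications are priced from a wholesale index, and the last step is "Once all costs are compiled and summed, they will be adjusted to constant dollars using the medical care component of the Consumer Price Index". The method ends at a total.

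Both arms are offered the programme. Under section 3.1 Number of Subjects, 300 participants receive it at once and "the other 300 will receive the intervention after 6 months". Section 4.6.2 describes how the waiting arm is brought in: "Starting 3 weeks before their 6-month time point, study staff will call patients to schedule a counseling appointment".

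Three other places bear on the question. Section 4.5 has the study database store each randomisation result. Section 5.1 says "we will calculate the number of counseling sessions completed", as a measure of acceptability and feasibility. Section 5.2 Data Monitoring Plan says "Counselors will also keep standardized, electronic documentation of every counseling session in a REDCap database created for the study".

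**The concern.** A per-patient figure needs a numerator and a denominator, and section 5.1 supplies only the first. Because everyone is eventually offered the programme, the cost could be divided by all 600 randomised, by the 300 in the immediate arm (using that arm's cost), or by those who start counselling. The first two give the cost per smoker offered the programme; the third gives the cost per smoker served. They agree only if everyone starts.

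The numerator also looks unfinished. The plan intends to sum all time but logs one week a month, and it states neither how one becomes the other nor how the week is picked. If the sampled weeks were systematically busy or quiet, or if the logged hours were added up unscaled, the total would be wrong. One of the trial's three aims therefore seems impossible to reproduce from the text.

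**Working it through.** **Inputs from the documents.** 300 + 300 = 600 participants (sections 2.3 and 3.1); one sampled week per month (section 5.1). The documents give no uptake, hours, labour share or per-patient cost, so there is no planned figure to reproduce. Everything marked as assumed below is illustration.

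**1. Denominator.** Let c be the cost per starter, s1 the share of the immediate arm who start, and s2 the share of the waiting arm who start. Assume cost is proportional to starters.

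- Per randomised participant, both arms: c(s1 + s2)/2
- Per randomised participant, immediate arm only: c × s1
- Per starter: c
- Ratio of per starter to per randomised (both arms): 2/(s1 + s2), which is 1/(mean share who start)

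With c = $500 (assumed):

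| s1 / s2 (assumed) | Per randomised, both arms | Immediate arm | Per starter | Ratio |
|---|---|---|---|---|
| 100% / 100% | $500 | $500 | $500 | 1.00 |
| 90% / 70% | $400 | $450 | $500 | 1.25 |
| 80% / 80% | $400 | $400 | $500 | 1.25 |
| 70% / 40% | $275 | $350 | $500 | 1.82 |
| 60% / 30% | $225 | $300 | $500 | 2.22 |

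Over mean shares from 95% to 30% the ratio runs from 1/0.95 = 1.05 to 1/0.30 = 3.33. Any headline range is therefore a choice of uptake and not a property of the design.

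The waiting arm is not the main source either. The ratio splits into 1/s1, which arises in the immediate arm alone, times 2 × s1/(s1 + s2), which the waiting arm adds:

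- 90%/70%: 1.11 × 1.13 = 1.25
- 70%/40%: 1.43 × 1.27 = 1.82
- 60%/30%: 1.67 × 1.33 = 2.22

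The 80%/80% row shows the same 1.25 with no difference between arms.

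Dividing two-arm cost by 300 would inflate the figure by 600/300 = 2.0. That would be a mismatch of numerator and denominator, which nothing in the plan calls for. Immediate-arm cost over 300 is consistent.

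**2. Scaling.** Sampled share of weeks: 12/52 = 23.1%, so the multiplier is 52/12 = 4.33. Using 4 instead would give 4/4.33 = 0.92, or staff cost about 8% low. Omitting the multiplier would understate labour about 4.3-fold, but only if an analyst treated something the plan calls a sample as a full count.

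**3. Choice of week.** Let labour be 50% to 90% of total cost (assumed).

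- Sampled weeks 20% off in the same direction every month: 0.20 × 0.50 = 10% to 0.20 × 0.90 = 18% of total cost.
- Sampled weeks varying independently with a 20% SD (assumed), over 12 months: 20%/√12 = 5.8% of labour, which is 5.8% × 0.50 = 2.9% to 5.8% × 0.90 = 5.2% of total cost.

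The larger figure needs a systematic cause. Section 5.1 lets staff tailor the entry form; it does not say they choose the week.

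**4. What can still be computed at analysis.** The stored allocation gives the number randomised by arm. The record of every session gives the number of starters and of sessions. Sampled time per activity can be multiplied by those session counts, which reduces dependence on how busy the sampled week was. It does not remove it, because time per session may vary with workload and because sessions 3 to 9 may be held by phone.

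**The case for a change.** The strongest case for a change is about timing. A denominator fixed before uptake is known cannot be chosen for the figure it gives, and two or three sentences would settle it. The choice of sampled week belongs to data capture and cannot be repaired afterwards. The counts exist in REDCap, but nothing in the text ties them to the cost analysis.

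Part of this stands. The text does omit all three items, and week selection is the one that later analysis could not fully recover. The rest carries little weight. Aim 2 is a descriptive estimate in a pilot, and section 5.1 sets no test, threshold or cost-effectiveness ratio that depends on it. The two denominators answer two legitimate questions, and neither is biased for its own question. Reporting both removes any room for selection at no cost in data.

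Two arguments that would raise the stakes lack support in the documents. None of the sections says that uptake will be lower after the wait; section 4.6.2 describes active scheduling calls. None makes cost an input to Aim 3, whose stated source is the staff interviews.

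**Conclusion.** No change is needed. Section 5.1 leaves detail unstated but gives no rule that produces a wrong result, and competent analysts would fill the gap from records the trial already keeps. The denominator effect is 1/(share who start), of unknown size because uptake is not given. The scaling step is routine. The choice of week matters only if the sampled weeks are consistently atypical, which the plan gives no reason to expect. The percentages rest on the assumed 20% deviation and 50% to 90% labour share, and the fold differences on assumed uptake with cost proportional to starters. Naming the denominators in the final report, with the scaling used, is ordinary good reporting.
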